3.1.6 Pharmacokinetic variables

Not applicable.

3.1.7 Pharmacogenomics endpoints

Pharmacogenetics endpoints and analyses will be detailed in a separate SAP.

3.2 DISPOSITION OF PATIENTS

This section describes patient disposition for both patient study status and the patient analysis populations.

Screened patients are defined as any patient who met the ACS inclusion criteria and signed the informed consent (ie, patients entering the run-in phase).

Randomized patients consist of all screened patients, with a double-blind treatment kit number allocated and recorded in the interactive voice response system (IVRS)/ interactive web response system (IWRS) database, regardless of whether the treatment kit was used or not. Patients treated without being randomized or treated with a double-blind treatment kit before the randomization will not be considered as randomized and will not be included in any analysis population.

For patient study status, the total number of patients in each of the following categories will be presented in the clinical study report using a flowchart diagram or summary table:

- Screened patients;
- Screened failure patients and reasons for screen failure;
- Non-randomized but treated patients, if any;
- Randomized patients;
- Randomized but not treated patients and reason for not being treated;
- Randomized and treated patients;
- Patients who completed the double-blind study treatment period as per protocol (as per e-CRF end-of-treatment form);
- Patients who did not complete the double-blind study treatment period as per protocol (as per e-CRF end-of-treatment form);
- Patients who discontinued the double-blind study treatment by main reason for permanent treatment discontinuation (as per e-CRF end-of-treatment form);
- Status at last study contact.

For all categories of patients (except for the screened and non-randomized categories) percentages will be calculated using the number of randomized patients as the denominator.

Reasons for treatment discontinuation will be supplied in tables giving numbers and percentages by treatment group. For blinded discontinuation due to low LDL-C level (patients who switched to placebo in blinded manner), the reason reported by the investigator will be reclassified as "2 consecutive LDL-C <15mg/dL (<0.39 mmol/L)".

Number (%) of patients who discontinued the follow-up for CV events will be summarized over time. The main reason for study discontinuation will be summarized overall and according to whether or not the patients had a primary efficacy endpoint confirmed by CEC prior study discontinuation.

A patient will be considered as having discontinued the follow-up for CV events if the date of the last information on efficacy endpoints (presence or absence) is before the common study end date.

Kaplan-Meier plots/estimates of the cumulative incidence of premature IMP treatment discontinuation due to any reason, or due to adverse event will be provided on randomized population. Not treated patient will be considered with event at Day 1 (day of randomization). All completers will be considered as right-censored observations. Time to premature IMP treatment discontinuation and censoring time will be defined as: Date of last IMP injection – Date of randomization + 14 days.

All major deviations potentially impacting efficacy analyses, randomization, and drug-dispensing irregularities, and other major deviations will be summarized in tables giving numbers and percentages of deviations by treatment group. These deviations are listed in the data review and surveillance plan.

Additionally, the following populations will be summarized by treatment group.

- Randomized population;
- Efficacy population: intent-to-treat (ITT) population;
- Safety population;
- Anti-alirocumab antibody population.

Definition of the study populations are provided in Section 3.3.

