### 6.2.2 Determination of end of clinical trial (all patients) - Common Study End Date

All randomized patients will be followed up until the Common Study End Date (CSED) visit, which is the final study visit (and a clinic visit) to be scheduled for each patient within 30 days of the CSED (see [Section 10.1.5.4](#)).

The CSED is defined as the date corresponding to 24 months after the closing of randomization ex-China (last date of randomization in all countries except China) or date when the target number of events (1613) is reached, whichever comes last.

- *Closing of randomization ex-China* will occur shortly after a total of 18,000 patients have been randomized (these may or may not include some patients randomized in China).

*Closing of randomization in China* will occur shortly after a total of 600 patients have been randomized in China or at the common study end date (see [Section 6.2.2](#)), whichever comes first.

Therefore, at the end of the double-blind treatment period, the overall randomized population will include about 18,000 patients who have either died or been followed for a minimum of 24 months, supplemented with an additional subset of patients from China (~600) who may be followed for less than 24 months.

**NOTE:** Common study end date is not dependent on the situation in China, and therefore will apply, regardless of Clinical Trial Authorization status and randomization status in China.

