3.1.3 Efficacy endpoints

3.1.3.1 Primary efficacy endpoint(s)

The primary efficacy endpoint is the time from randomization to first occurrence of 1 of the following clinical events, as determined by the CEC:

- CHD death (including "undetermined causes of death" as per the CEC);
- Any non-fatal MI;
- Fatal and non-fatal ischemic stroke (including "stroke not otherwise specified" as per the CEC);
- Unstable angina requiring hospitalization.

The rules to determine the components and the date of the event that will be considered in the analyses of the primary efficacy endpoint are detailed in Appendix C.

If none of these events is observed at the time of the analysis cut-off date (final or interim, depending on the timing of the analysis, see Section 3.4.4.1 and Section 4 for details), the patient will be right-censored at the date of last contact when information on efficacy endpoints (presence or absence) has been retrieved, or at the date of death, or at the cut-off date/CSED, whichever comes first.

The last information on efficacy endpoint (presence or absence)" will be the latest date among:

- The date of last visit performed with "endpoints events" e-CRF page completed.
- The "Date of last information on efficacy endpoint (presence or absence)" reported in the visit e-CRF pages during the course of the study.
- The "Date of last information on efficacy endpoint (presence or absence)" reported at the end of the study for all patients (this information can also be completed during the course of the study for "lost-to-follow-up" patients, patients who discontinued the follow-up, and patients who died).

In case of no information on the presence or absence of efficacy endpoint, nor on death at time of database extraction for the interim analyses, the censoring date will be the randomization date (eg, for patients randomized but having not reached the Month 1 visit yet).

Handling of missing or incomplete dates

In the exceptional circumstances when the exact date of occurrence of the outcome event has not been established (day and/or month missing), the date will be imputed as follows:

Table 4 - Imputation of incomplete date of events composing the primary efficacy outcome

Type of event	Imputed date
	Only the day is missing
Death	The latter of the last contact date + 1 day and the 1 st day of the month.
Other primary endpoint component (CHD event or ischemic stroke)	The latter of the randomization date and the 1^{st} day of the month.

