3.4.4.1 Analysis of primary efficacy endpoint(s)

The analysis of the primary efficacy endpoint will be the comparison between the two treatments using a log-rank test stratified by region (North America, South America, Western Europe, Eastern Europe, Asian, Other). The randomization is stratified by country but since the number of events per individual country is expected to be low (about 50 countries), the analysis will be stratified according to a grouping of countries into regions.

This primary comparison will be the 1-sided test (at 0.0249 type 1 error for the final analysis) of the following hypotheses at the final analysis:

H₀: HR \geq 1 versus H₁: HR <1

The estimates of the HR and corresponding confidence interval (CI) at $(1-2\alpha)$ % level (α being the 1-sided significance level: α =0.0249 at final analysis, α =0.0001 at second interim analysis) will be provided using a Cox Proportional Hazard model stratified by region. The underlying assumption of proportional hazards for Cox model will be checked by visual inspection of Kaplan-Meier plots. If proportionality is not observed, sensitivity analyses will be performed. In particular, the results will be presented by yearly intervals: the number of events per 100 patient-years for each yearly interval will be provided for each treatment group as well as the ratio of the two event rates. In addition, between-treatment cumulative rate ratios based on the Kaplan-Meier estimates and the corresponding 95% CIs) will be provided at yearly interval.

The cumulative incidence rate over time (at 6 months and by year) together with appropriate interval will be estimated by treatment group using Kaplan-Meier estimates.

Reasons for censoring (including patient who died before the cut-off date/CSED for other reason than CHD, lost to follow-up) will be summarized. For patients censored before the cut-off date/CSED, time from last contact when information on efficacy endpoints has been retrieved to cut-off date will be summarized.

Interim analyses

Two interim analyses will be performed. See Section 4 for description of these analyses. The cut-off dates of final (ie, CSED) and interim analyses are expected to be:

- First interim analysis date (futility): when 807 patients have experienced at least 1 primary efficacy event (50% fraction information);

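### SAP 3.2 counts every patient who dies before the common study end date as having discontinued CV follow-up, so the completeness summaries mix mortality with true loss

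*SAP*

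**What the plan says.** SAP 3.2 (Disposition of patients) plans this summary: "Number (%) of patients who discontinued the follow-up for CV events will be summarized over time". It then defines the count by one test. A patient has discontinued CV follow-up "if the date of the last information on efficacy endpoints (presence or absence) is before the common study end date". Death is not mentioned.

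SAP 3.1.3.1 defines the date used in that test as the latest of several recorded dates. One of them is filled in for all patients at the end of the study, and may be completed earlier for those lost to follow-up, "patients who discontinued the follow-up, and patients who died". Patients who died therefore carry this date too, and they are named as a group apart from the other two.

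SAP 3.4.4.1 adds two summaries for the primary endpoint. The first is of reasons: "Reasons for censoring (including patient who died before the cut-off date/CSED for other reason than CHD, lost to follow-up) will be summarized". The second concerns everyone censored before the cut-off date or CSED: "time from last contact when information on efficacy endpoints has been retrieved to cut-off date will be summarized".

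Protocol 6.2.2 describes the main part of the final population as "patients who have either died or been followed for a minimum of 24 months", and SAP 1.3 says much the same.

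**The concern.** How completely endpoints were followed up is a basic check on whether the intention-to-treat event counts can be relied on. A patient followed to death has no missing endpoint time. A patient who left contact two years before the CSED does. The rule in SAP 3.2 gives both the same label.

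The gap summary in SAP 3.4.4.1 has the same weakness. Take a patient randomized 56 months before the CSED who dies of a non-CHD cause at month 6. That patient contributes a gap of 50 months, although no follow-up was missed.

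This matters here because CHD death, CV death and all-cause mortality are all main secondary endpoints (SAP 3.1.3.2.1), so the trial is looking for a mortality difference. A completeness figure that absorbs deaths will move with any such difference. Read alone, it could resemble differential drop-out or offset a real imbalance in loss.

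**Working it through.** **Logic of the rule**

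1. Rule (SAP 3.2): discontinued if the last efficacy-information date is earlier than the CSED.
2. For a patient who dies before the CSED, that date is on or before the date of death. The SAP does not say what date the site enters; I assume it is not later than death.
3. So the last efficacy-information date ≤ death < CSED, and the rule is met whatever the quality of follow-up.
4. A patient who dies after the CSED with information up to the CSED does not meet the rule. SAP 3.1.4.2 keeps deaths after the CSED as their own category.
5. Elsewhere the plan sets death apart. SAP 3.1.3.1 lists it separately from loss and from discontinued follow-up, and makes the date of death a censoring point in its own right. SAP 1.3 and Protocol 6.2.2 put patients who died alongside those followed for the minimum period. The definition in 3.2 is the exception.

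**Size**

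The plan gives no figure for this count and no all-cause mortality rate, so there is nothing to reproduce and the size can only be illustrated.

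Inputs:
- Enrolment by month from SAP Table 1. At face value it sums to 18,244 (2,004 + 29 × 560); I scaled it to 18,000.
- CSED at month 64 (SAP 1.1).
- Loss of 1% at 24 months (SAP 1.3), taken as a constant hazard: L = −ln(0.99)/24 = 0.000419 per month. The SAP states this for loss before a primary endpoint; applying it to all follow-up is an assumption.
- Death hazard D = r/12 per month, with r = 0.5% to 2% per year. This is an assumption.

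Mean potential follow-up is 40.4 months (about 60,600 patient-years). Ignoring deaths, Σ n(1 − exp(−L·f)) gives about 302 patients lost by the CSED (1.7%), where n is the number enrolled in a month and f their potential follow-up.

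With deaths as a competing exit, total exits are Σ n(1 − exp(−(D+L)·f)), split in the ratio D : L.

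| Assumed deaths per year | Deaths before CSED | Truly lost | Count under SAP 3.2 | % of 18,000 |
|---|---|---|---|---|
| 0.5% | 298 | 299 | 597 | 3.3 |
| 1.0% | 590 | 297 | 887 | 4.9 |
| 1.5% | 878 | 294 | 1,172 | 6.5 |
| 2.0% | 1,160 | 291 | 1,451 | 8.1 |

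True loss stays at about 1.6% to 1.7% throughout. The overstatement factor is (D+L)/L. At 1% per year it is 1 + 0.000833/0.000419 ≈ 3.0; over the range it runs from about 2 to about 5.

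The table also shows the effect on an arm comparison. If one arm had deaths at 1.0% per year and the other at 1.5%, the rule would give 4.9% and 6.5%, although true loss is about 1.6% in both. This is an illustration, not a forecast.

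**The case against.** The definition feeds only a descriptive table, and other planned output helps to separate death from loss. SAP 3.2 also lists "Status at last study contact" and states: "The main reason for study discontinuation will be summarized overall", with a split by whether a confirmed primary endpoint came first. SAP 3.4.4.1 names non-CHD death and loss to follow-up as different reasons for censoring. Deaths are tabulated in SAP 3.4.5.2 and all-cause death is a main secondary endpoint. A careful reader could therefore work out much of the true loss.

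Most of this stands, and it limits the point. It does not remove it. The categories for reason and status are not listed, so death is neither promised nor ruled out there. The split by prior endpoint leaves deaths without a primary event in the same stratum as true loss. The censoring-reason table separates the two causes, but the gap summary that follows it does not.

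Three stronger inferences are tempting and are not supported:
- That the primary result is biased. Primary-endpoint censoring has its own rule in SAP 3.1.3.1, which names the date of death.
- That the figure will be set against the 1% loss in the sample size and appear to breach it. Neither document plans that comparison. The 1% is loss before a primary endpoint at 24 months, a different quantity even after correction.
- That the Protocol formally defines death as complete follow-up. Section 6.2.2 describes who will be in the population at study end; it is not a definition of completeness.

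**Conclusion.** The point holds for the descriptive completeness summaries only. As written, SAP 3.2 counts every death before the CSED as discontinued CV follow-up, and the gap summary in SAP 3.4.4.1 includes patients censored at a non-CHD death. Both figures mix mortality with true loss. Where they are shown by arm, which the sentence in 3.2 does not itself state, they will differ whenever mortality does, other things equal.

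Under assumed mortality of 0.5% to 2% per year, constant hazards and the SAP's enrolment and loss assumptions, the literal count would be about 3.3% to 8.1% of 18,000 patients, against about 1.6% to 1.7% truly lost. The direction follows from the wording; the size rests on the assumed death rate. It would be wrong to say that the figure must mainly reflect mortality: at 0.5% per year, deaths and losses are about equal.

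The log-rank test, hazard ratio, event target of 1613 and power are not affected. This should be corrected because a stated rule gives a misleading figure, but it does not threaten the trial's main conclusion.

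**What to change.** - **SAP 3.2:** define discontinued CV follow-up as last efficacy information before the earlier of the CSED and the date of death. This is better than excluding everyone who died. Protocol 10.3.4 and 10.3.5 ask sites to recover vital status for patients who withdrew or stopped attending, so some will be lost first and later found to have died. They should still count as incomplete, and under this wording they do.
- **SAP 3.4.4.1:** measure the gap from last efficacy contact to the earlier of death and the cut-off date/CSED.
- **Disposition table:** show deaths before the CSED as a separate category by arm.
- **Derivation note:** SAP Table 4 imputes an incomplete death date to at least one day after last contact. State how such deaths are classified, so that the imputation alone does not make them incomplete.

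The cost is a clause in each section and a small change to the derivation code. It uses dates already collected and changes no inferential analysis.

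### One Kaplan-Meier rule set serves both the any-reason and the adverse-event discontinuation curves; taken literally, it overstates the adverse-event curve

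*SAP*

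**What the plan says.** SAP Section 3.2 (Disposition of patients) states that Kaplan-Meier plots or estimates of the "cumulative incidence of premature IMP treatment discontinuation due to any reason, or due to adverse event will be provided on randomized population". Three rules follow, and none is limited to one of the two curves. The first two read: "Not treated patient will be considered with event at Day 1 (day of randomization). All completers will be considered as right-censored observations". So never-treated patients are events on the day they are randomized, and completers are the only patients named as censored. The third is a single formula that sets the time for events and censorings alike: "Time to premature IMP treatment discontinuation and censoring time will be defined as: Date of last IMP injection" minus the randomization date, plus 14 days.

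The SAP does not say how a patient who stops for a non-AE reason, or who dies on treatment, enters the AE curve. It names no competing-risk estimator.

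Three other statements in the same section bear on the point. The disposition listing includes "Randomized but not treated patients and reason for not being treated", so the reason will be known. "Reasons for treatment discontinuation will be supplied in tables giving numbers and percentages by treatment group". And the blinded switch to placebo after two consecutive LDL-C values below 15 mg/dL counts as a discontinuation with its own non-AE label, replacing whatever reason the investigator gave. Only patients randomized to alirocumab can be switched. Under SAP Section 3.5.1 their last dose is the last active injection.

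**The concern.** For the any-reason curve the rules are coherent: every stop is an event, and a patient who never starts can reasonably be treated as stopping at once. The AE curve raises two problems.

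First, the Day-1 rule assigns never-treated patients to the AE event whatever the reason they were not treated.

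Second, a patient who stops for another reason can no longer have a first permanent discontinuation because of an AE. That is a competing event. Censoring it makes one minus Kaplan-Meier estimate what would happen if nobody stopped for other reasons, and not the proportion who actually stop for an AE. The SAP calls the quantity a cumulative incidence, which is the latter.

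At stake is the absolute level of a by-arm tolerability curve. There is also a practical problem: the AE curve cannot be programmed from the text without a decision that the text does not make.

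**Working it through.** **Inputs.** The estimator, the Day-1 rule, the censoring rule and the time formula come from SAP Section 3.2. The 64-month study duration comes from SAP Section 1.1 and the accrual schedule from SAP Table 1. The documents state no discontinuation rate and no never-treated rate, so there is no planned figure to reproduce. All rates below are assumptions.

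**How a non-AE stop can enter the AE curve.**

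1. Counted as an event, because only completers are named as censored. The AE curve then becomes the any-reason curve.
2. Censored at last injection plus 14 days. The competing event is then treated as uninformative censoring.
3. Kept event-free to the common study end date. This would remove the bias, but the stated censoring time does not allow it.

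Option 2 is the natural reading and is the one quantified.

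**Formulas.** Let A and B be the true 48-month proportions of treated patients stopping for an AE and for other reasons, and f the share never treated. With constant cause-specific hazards:

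- Total cumulative hazard: H = −ln(1 − A − B)
- AE part: H_AE = H × A/(A + B)
- Curve under the SAP rules: 1 − (1 − f) × exp(−H_AE)
- Aalen-Johansen cumulative incidence, never-treated patients counted as competing events: (1 − f) × A

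**Worked case, A = 4%, B = 10%, f = 0.** H = −ln(0.86) = 0.1508. H_AE = 0.1508 × 4/14 = 0.0431. The curve reads 1 − exp(−0.0431) = 4.22%, against a true 4.00%.

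**With f = 0.5%.** The curve reads 1 − 0.995 × 0.9578 = 4.70%, against 0.995 × 4% = 3.98%. Of the 0.72-point gap, about 0.22 comes from censoring and about 0.50 from the Day-1 rule. Under option 1 the same case would read 1 − 0.995 × 0.86 = 14.4%.

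| AE / other at 48 months | Never treated | Curve under SAP rules | Aalen-Johansen | Excess (points) |
|---|---|---|---|---|
| 4% / 10% | 0 | 4.22% | 4.00% | 0.22 |
| 6% / 14% | 0 | 6.48% | 6.00% | 0.48 |
| 8% / 22% | 0 | 9.07% | 8.00% | 1.07 |
| 4% / 10% | 0.1% | 4.31% | 4.00% | 0.32 |
| 4% / 10% | 0.5% | 4.70% | 3.98% | 0.72 |
| 6% / 30% | 1% | 8.10% | 5.94% | 2.16 |

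(Excesses are taken before rounding.)

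**Range.** Over AE stopping of 2–6%, other stopping of 5–30% and 0.1–1% never treated, the excess runs from 0.15 to 2.16 points. With the Day-1 rule removed (f = 0) it runs from 0.05 to 1.17 points. With 0.1% never treated and other stopping of at most 10%, it does not exceed 0.43 points.

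**Simulation check.** On the SAP Table 1 accrual schedule, with administrative censoring at month 64 and about 180,000 simulated patients, the 4%/10%/0.5% case gave 4.71% against 3.99%. The 6%/30%/1% case gave 8.05% against 5.91%. Both agree with the closed form.

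**The case against.** The strongest reply is that the SAP is being read too literally. The Day-1 and completer sentences fit the any-reason curve and may have been meant only for it. The AE curve's event is already limited by its own name, and the reason for not being treated is collected. This is fair as to intent. But the text does not restrict the rules, and it leaves non-AE stops undefined in the AE curve on any reading.

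Further points stand in whole or in part:

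- A reader might infer that no never-treated patient can be an AE stop. The documents do not support that. AEs are recorded from consent, and SAP Section 3.4.5.1 plans a table of pre-treatment AEs that led to discontinuation. A never-treated patient whose recorded reason was an AE is a legitimate event.
- The never-treated share should be small, because the first injection is given on site at the randomization visit (Protocol Sections 8.1.2 and 10.1.5.1.1). The 0.5% used above is an assumption.
- A reader might take a mismatch between the curve and the n (%) table as proof of the error. With staggered entry and roughly 24 to 64 months of planned follow-up, a time-specific estimate need not match a crude percentage under any estimator.
- A reader might also infer a biased comparison between arms. With non-AE stops censored and constant hazards, the curve for treated patients depends only on the AE hazard, so equal AE hazards give equal curves whatever the other-reason rates. Aalen-Johansen curves would then differ if other-reason stopping differed. For comparing arms the choice is partly one of estimand; for absolute risk, which is what cumulative incidence means, Aalen-Johansen is the right estimator.

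**Conclusion.** The point holds for the AE curve on the literal text. If non-AE stops are censored, one minus Kaplan-Meier cannot fall below the cumulative incidence of AE discontinuation and will normally exceed it. That direction does not depend on the assumed rates; the size does. With few never-treated patients and modest other-reason stopping, the excess is probably under about half a percentage point. It passes one point only with heavy other-reason stopping or a never-treated share near 1%.

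A reader might conclude that the trial's reporting of AE discontinuation as a whole is inflated. The documents do not support that. The curve is a descriptive disposition output with no stated test. The by-reason n (%) table is unaffected, as are the summaries of treatment-emergent AEs leading to discontinuation (SAP Section 3.4.5.1), which are based on the safety population and so exclude patients who received no dose. This is a contained error of estimator and rule, worth correcting because the remedy is cheap.

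**What to change.** In SAP Section 3.2, limit the Day-1 rule, the censoring of completers and the Kaplan-Meier estimator to the any-reason curve. For the AE curve, specify:

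- the Aalen-Johansen cumulative incidence, with completers censored as now;
- all non-AE stops as competing events, including death not recorded as an AE stop and the blinded LDL-C switch to placebo, which arises only in the alirocumab group;
- never-treated patients classified by recorded reason: an AE event only if that reason was an AE, otherwise a competing event on Day 1. Alternatively, show the AE curve in treated patients only.

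The cost is two or three sentences and a standard procedure option, with no new data and no effect on alpha or any efficacy result. The stated AE-discontinuation percentages become slightly lower. Differences between arms in the curve will then also reflect other-reason stopping, including the switch, and a footnote should say so.
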